5.3. Randomization and blinding

5.3.1. Randomization and blinding

The first part of the study was divided into open-label studies without randomization and blinding.

The second part of the study was a randomized double-blind study. The investigator will enter the Interactive Web Response System (IWRS) after confirming that the subject meets all inclusion and exclusion criteria. The IWRS will assign a randomization number that associates the subject with a treatment group and assigns a specific treatment to the subject who should receive study treatment within 3 days of randomization, including the day of randomization. Subjects were randomized to Trilaciclib or placebo in a double-blind 1:1 ratio, stratified by 1st line vs 2nd/3rd line ES-SCLC, ECOG PS (0-1 vs 2), and presence vs absence of brain metastases. Investigators involved in the trial (including investigators, sponsor personnel, contract research organization personnel, central pathology reviewer, biological sample analysts, etc., and subjects were blinded to which drug treatment was assigned. The investigator obtained the subject 's assigned randomization number based on the information provided by the IWRS.

Specific blinding procedures are described in the Drug Administration Manual.

5.3.2. Unblinding

Unblinding may be performed in emergency situations. Emergency unblinding should be the last category of measures to deal with emergencies associated with the medication and/or dose administered to the subject. If unblinding is necessary for safety reasons (e.g., serious adverse events, etc.) to treat a subject, it is recommended that the sponsor 's medical monitor be contacted prior to unblinding and the investigator unblinding the subject via the IWRS system. Once unblinded, the subject discontinued study treatment. The investigator should record this event in the original medical records and inform the sponsor 's clinical medical director as soon as possible.

For the purpose of regulatory reporting, the Sponsor PV will unblind the treatment code if required by health authorities for all serious, unexpected suspected adverse events considered related to the study drug by the investigator or sponsor, etc., but the Sponsor study team remains blinded.

In the second part, when the primary analysis is performed for the primary endpoint, the

necessary sponsor personnel will be unblinded and the investigator, subjects and other personnel will continue to be blinded; at the final analysis, the study will be unblinded.

5.4. Study treatment modification

5.4.1. Dose modification for trilaciclib/placebo

Based on previous clinical studies with Trilaciclib and considering that the risk of inadequate HSPC stagnation is minimized as much as possible, the dose of Trilaciclib/placebo will not be adjusted and remains at 240 mg/m² in this trial unless safety data in Part I suggest that the dose of Trilaciclib/placebo needs to be adjusted.

Refer to Section 5.5.1.1 for dose interruptions and terminations of Trilaciclib.

5.4.2. Dose modification for chemotherapy agents

Carboplatin, etoposide, and topotecan should meet neutrophil $\ge 1.5 \times 10^9$ /L and platelet count $\ge 100 \times 10^9$ /L before dosing on the first day of the second and subsequent cycles, and all drug-related nonhematologic toxicities (except alopecia) need to recover to Grade 1 or lower or baseline levels. Dose modifications on the first day of the second and subsequent cycles are shown in Table 5, and no more than two dose reductions are allowed (concurrent carboplatin and etoposide dose reductions are one dose reduction), dose reductions are unidirectional permanent, and no dose increases are allowed. Delays in chemotherapy cycles of up to 1 week due to operational reasons such as legal holidays and up to 2 weeks due to treatment toxicity may be permitted; however, if the investigator believes that a delay of more than 2 weeks is beneficial to the subject, dosing may be delayed for more than 2 weeks upon request by the investigator and medical review and written approval by the sponsor.

Dose Level	Etoposide (mg/m ²)	Carboplatin (AUC)	Topotecan (mg/m ²)
Dose level-1	Reduce to 75	Decreased to $AUC = 4$	1
Dose level-2	Reduce to 50	Decreased to $AUC = 3$	0.8

 Table 5 Dose reductions for carboplatin, etoposide and topotecan

Note: Simultaneous dose reduction of carboplatin and etoposide is defined as one dose reduction

5.4.2.1. Dose modifications based on hematologic toxicities

Dose modifications were based on various hematologic toxicities occurring during Cycle 2 and on Day 1 of subsequent cycles as follows:

Table 6 Dose Modification Based on Neutrophil Count and Platelet Count

Neutrophil count < 1.5 x 10 ⁹ /L	Carboplatin, etoposide and topotecan
---	--------------------------------------

First occurrence	Without dose adjustment, G-CSF was used according to the 2019 edition of Expert Consensus on Diagnosis and Treatment of Neutropenia Caused by Cancer Chemotherapy
Second occurrence	First Dose Reduction
Third occurrence	Second Dose Reduction
Fourth occurrence	Drug withdrawn
Platelet count < 100 x 10 ⁹ /L	Carboplatin, etoposide and topotecan
Second occurrence	First Dose Reduction
Third occurrence	Second dose reduction
Fourth occurrence	Drug withdrawn

Table 7 Dose Modification Based on Absolute Trough Neutrophil Count with or without

Absolute neutrophil count trough	Carboplatin, etoposide and topotecan		
Grade 3 or 4 < 7 days (no fever)	No dose adjustment		
Grade 4≥7 days (no fever)			
First occurrence	Without dose adjustment, G-CSF was used according to the 2019 edition of Expert Consensus on Diagnosis and Treatment of Neutropenia Caused by Cancer Chemotherapy		
Second occurrence	First Dose Reduction		
Third occurrence	Second Dose Reduction		
Fourth occurrence	Drug withdrawn		
Grade 3/4 (fever)			
First occurrence	Without dose adjustment, G-CSF was used according to the 2019 edition of Expert Consensus on Diagnosis and Treatment of Neutropenia Caused by Cancer Chemotherapy		
Second occurrence	First Dose Reduction		
Third occurrence	Second Dose Reduction		
Fourth occurrence	Drug withdrawn		

Fever

Table 8 Dose Modification Based on Trough Platelet Values

Platelet count	Carboplatin, etoposide and topotecan
➢ Grade 3 combined	
bleeding or Grade 4	
	No dose adjustment, recombinant human interleukin-11, rhIL-11
	derivatives, recombinant human thrombopoietin or platelet
First occurrence	transfusions were used according to the 2019 Chinese Expert
	Consensus on Diagnosis and Treatment of Thrombocytopenia
	Associated with Cancer Chemotherapy
Second occurrence	First Dose Reduction
Third occurrence	Second Dose Reduction
Fourth occurrence	Drug withdrawn

5.4.2.2. Dose Modifications Based on Nonhematologic Toxicities

5.4.2.2.1. Hepatotoxicity

Dose modifications were based on hepatotoxicity occurring on the first day of the second and subsequent cycles as follows:

ALT/AST		Bilirubin	Carboplatin, etoposide and topotecan
Grade 1	AND/OR	\leq Grade 2	No change
Grade ≥ 2 a First occurrence Second occurrence Third occurrence	AND/OR	Grade ≥ 3 First occurrence Second occurrence Third occurrence	First Dose Reduction Second dose reduction Drug withdrawn

Table 9 Dose Modifications Based on ALT/AST and Bilirubin

A If liver metastasis is present at baseline and ALT/AST is Grade 2, a 1-grade worsening of the AE grade will result in a reduction of the first dose. If combined ALT/AST/combined bilirubin abnormalities occur, dose reduction is judged based on more severe cases.

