5.4.2.3. Other toxicities

For the first occurrence of any nonhematologic Grade 2 chemotherapy-related toxicity (except alopecia), all study treatment should be withheld until the toxicity recovers to Grade 1 or baseline. Treatment may then be resumed at the same dose level. For the second occurrence of any nonhematologic Grade 2 chemotherapy-related toxicity (except alopecia), treatment should be resumed at a reduced dose level following recovery of the toxicity to Grade 1 or baseline; for the third occurrence, the dose should be reduced to Dose Level 2. A fourth occurrence will lead to discontinuation of carboplatin, etoposide and topotecan treatment. For Grade 1 toxicities, the dose should not be reduced.

For any Grade 3 or 4 chemotherapy-related toxicity not mentioned above, all study treatments should be withheld until the toxicity recovers to Grade 1 or baseline. Treatment should then be resumed at the first appearance with the first dose reduction and at the second appearance with the second dose reduction. A third occurrence will lead to discontinuation of carboplatin, etoposide and topotecan treatment.

The above chemotherapy drug dose adjustment regimen is recommended by the study. If the investigator recommends different treatments in clinical practice, the investigator may select the adjustment regimen by referring to the corresponding package insert of chemotherapy drugs or clinical routine guidelines. In this case, it is necessary to clearly record the reasons for other adjustment regimens in the subject 's case and discuss with the sponsor if necessary.

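### For chemotherapy-related Grade 2 liver toxicity on Day 1 of Cycle 2 or later, Table 9 and the Grade 2 paragraph of Protocol 5.4.2.3 give two conflicting chemotherapy rules

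*Protocol*

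**What the plan says.** Protocol 5.4.2.2.1 states the scope of Table 9: "Dose modifications were based on hepatotoxicity occurring on the first day of the second and subsequent cycles". In the row for ALT/AST Grade 2 or higher (or bilirubin Grade 3 or higher), the first, second and third occurrences lead to "First Dose Reduction Second dose reduction Drug withdrawn". The row for ALT/AST Grade 1 and/or bilirubin up to Grade 2 makes no change. A footnote sets a different trigger, a one-grade worsening, for patients with liver metastases at baseline and Grade 2 ALT/AST. It also says that when both parameters are abnormal, "dose reduction is judged based on more severe cases".

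Protocol 5.4.2.3, headed as dealing with other toxicities, opens: "For the first occurrence of any nonhematologic Grade 2 chemotherapy-related toxicity (except alopecia), all study treatment should be withheld". The hold lasts until the event is back to Grade 1 or its baseline level, after which "Treatment may then be resumed at the same dose level". The ladder then steps down: a second episode means restarting at a lower level once recovered, a third means going down to Dose Level 2, and a fourth ends the chemotherapy. The next paragraph, on Grade 3 or 4 toxicity, is confined to toxicities not already covered; the Grade 2 paragraph has no such limit. The section closes by describing the scheme as recommended and letting the investigator use the package insert or routine guidelines instead, with reasons recorded.

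Protocol 5.4.2 adds a condition for dosing on Day 1 of Cycle 2 onwards: "all drug-related nonhematologic toxicities (except alopecia) need to recover to Grade 1 or lower or baseline levels". It allows at most two dose reductions, which are permanent.

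**The concern.** A patient with related Grade 2 ALT/AST on Day 1 of a later cycle satisfies the entry condition of both ladders. One site following the protocol reduces at the first episode; another, also following it, returns to the same dose. Because reductions are permanent and capped at two, that choice cannot be undone, and it also uses up part of the allowance for later toxicity. No passage says which rule prevails.

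This reaches the analysis through MAHE, a key secondary endpoint. All-cause chemotherapy dose reduction is one of its five components (Protocol 2.2), SAP 4.4.2.4 sums the component events, and SAP 4.6.1 identifies reductions by comparing actual doses between cycles. Stopping one episode earlier also shortens the treatment weeks or cycles used as the offset in that model. A site's reading of the protocol can therefore add or remove endpoint events.

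**Working it through.** The plan gives no figure to reproduce. The check sets the two rules side by side and counts cumulative dose reductions for one patient with successive related Grade 2 episodes, each present on Day 1 of Cycle 2 or later. A joint carboplatin and etoposide reduction counts as one, as in the note to Table 5.

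**Grade 2 ALT/AST, footnote trigger not applicable**

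| Episode | Table 9 | 5.4.2.3 | Cumulative reductions, Table 9 vs 5.4.2.3 | Difference |
|---|---|---|---|---|
| 1 | first reduction | same dose after recovery | 1 vs 0 | 1 − 0 = 1 |
| 2 | second reduction | reduced dose | 2 vs 1 | 2 − 1 = 1 |
| 3 | withdrawn | Dose Level 2 | 2 (stopped) vs 2 (still treated) | 2 − 2 = 0 |
| 4 | already stopped | discontinued | 2 vs 2 | 0 |

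A patient with a single episode has one MAHE dose-reduction event under Table 9 and none under 5.4.2.3. After three episodes the counts agree, but one rule has ended chemotherapy and the other has not.

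**Isolated Grade 2 bilirubin**

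| Episode | Table 9 | 5.4.2.3 | Cumulative reductions, Table 9 vs 5.4.2.3 |
|---|---|---|---|
| 1 | no change | same dose after recovery | 0 vs 0 |
| 2 | no change | reduced dose | 0 vs 1 |
| 3 | no change | Dose Level 2 | 0 vs 2 |
| 4 | no change | discontinued | 0 vs 2 (stopped) |

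Here the rules agree on dose at the first episode and part from the second, in the opposite direction to ALT/AST: Table 9 is now the rule that never reduces.

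**Other passages that might settle or widen the conflict**

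- Day 1 recovery criterion (5.4.2): this governs when dosing may restart, not at what dose. At a first Grade 2 bilirubin episode, waiting for Grade 1 or baseline and then giving the same dose satisfies 5.4.2, Table 9 and 5.4.2.3 together. It sits awkwardly with a table that assigns doses for hepatotoxicity present on Day 1, but it does not contradict either ladder.
- Overlapping Table 9 rows (Grade 2 ALT/AST with mildly abnormal bilirubin): the footnote settles these by the more severe abnormality.
- Hepatotoxicity in 5.5.1.1: this concerns trilaciclib, not chemotherapy.
- Primary endpoint: Table 9 begins on Day 1 of Cycle 2, so the choice of ladder acts after Cycle 1 DSN has accrued.

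**The case against.** The best defence is structural. Section 5.4.2.3 follows specific subsections on hematologic toxicity, hepatotoxicity, gastrointestinal effects and hypersensitivity, and its heading marks it as residual. If it governed hepatic Grade 2 events, the Grade 2 threshold for ALT/AST in Table 9 would do nothing for related events. Reading the specific rule over the general one is natural. It is not stated, however. The Grade 2 paragraph exempts only alopecia, while the next paragraph shows that the authors knew how to exclude toxicities already covered. A strictly residual reading also leaves a gap: 5.4.2.2.2 gives no dose rule for gastrointestinal toxicity, so excluding every listed toxicity would leave Grade 2 gastrointestinal events without one.

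Second, the scheme is only recommended, so variation between sites is allowed anyway. That stands as a limit on how much uniformity any rewording can achieve. It does not resolve the overlap: with two recommended ladders, neither site nor monitor can tell which choice is the deviation that needs a recorded reason.

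Third, the overlap is narrow. A mid-cycle Grade 2 event that has recovered by Day 1 falls only under 5.4.2.3, and the footnote changes the ALT/AST trigger for some patients with liver metastases. Both points stand.

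Fourth, MAHE counts reductions from any cause by design, and SAP 4.6.2 already summarises adverse events leading to dose reduction, delay or discontinuation, so hepatic reductions would not be hidden. This stands, and it makes any change to the SAP optional.

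**Conclusion.** The conflict is real but confined to two passages and to related Grade 2 ALT/AST or isolated Grade 2 bilirubin on Day 1 of Cycle 2 or later. Its size for a single patient with ALT/AST episodes is one dose-reduction event after one or two episodes, and stopping at the third rather than the fourth. This assumes that each episode is judged related and that the site follows one ladder throughout.

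Several stronger readings are tempting and are not supported:

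- A reader might count the Day 1 criterion as a third conflicting rule; it concerns timing and is compatible with either ladder.
- A reader might extend the third-versus-fourth stopping conflict to all Grade 2 liver toxicity; it holds for ALT/AST only.
- A reader might scale the effect from the all-cause reductions in Table 3, 30.3% on placebo and 8.9% on trilaciclib, which at 40 per arm is 40 × 0.303 = 12.1 and 40 × 0.089 = 3.6 patients. Those are overseas figures with no hepatic share, and the documents give no Grade 2 hepatotoxicity rate, so no number of affected patients per arm can be defended.
- A reader might infer bias in MAHE. Under double-blind randomisation a site's choice of ladder should not depend on arm, so the expected effect is noise of unknown size.

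The main reason to act is that each hepatic event should have one dosing and stopping rule. The effect on the analysis is secondary.

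**What to change.** Reconcile Table 9 with the Grade 2 paragraph of Protocol 5.4.2.3 so that every hepatic event, ALT/AST and bilirubin alike, falls under one stated chemotherapy rule, and say explicitly how the two sections relate. Check the resulting wording against the Day 1 recovery criterion in 5.4.2 and against the liver-metastasis footnote. Which rule applies is for the sponsor's clinical team; this review takes no position on it.

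Optionally, show MAHE dose reductions by reason (hematologic, hepatic, other), drawing on the adverse events leading to dose reduction that SAP 4.6.2 already summarises.

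The cost is protocol wording, which needs ethics committee approval under Protocol 11.4. The optional display is one split of an existing table. It needs no new data if the case report form links each reduction to its reason, which is assumed here. Nothing changes in the primary analysis or the sample size.

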5.4.2.2.2. Gastrointestinal side effects

Antiemetics and antidiarrheals may be used to control nausea, vomiting, and diarrhea.

Subjects were encouraged to take large oral rehydration fluids.

5.4.2.2.3. Hypersensitivity

For subjects who experience mild to moderate hypersensitivity reactions and have been

successfully managed, prophylaxis and bedside vital sign monitoring is recommended for all Version No.: V1.4, March 21, 2022 Confidential 63 / 111 subsequent doses.

- Mild symptoms (eg, mild flushing, rash, itching): complete the infusion. Bedside monitoring. No treatment required.
- Moderate symptoms (eg, moderate rash, flushing, mild dyspnea, chest discomfort): discontinue infusion. Diphenhydramine 25 mg and dexamethasone 10 mg were administered intravenously. The infusion was resumed at a low rate (20 mg/h) after recovery of symptoms. If no further symptoms appear after 15 min, the rate may be increased to full rate until the infusion is complete. If symptoms recur, the infusion must be stopped. Subjects should not receive additional chemotherapy during this cycle, but may receive doses for subsequent cycles at the investigator 's discretion.
- Serious life-threatening symptoms (eg, hypotension requiring vasopressor therapy, angioedema, respiratory distress requiring bronchodilator therapy, generalized urticaria): discontinue infusion immediately. Diphenhydramine and dexamethasone were administered intravenously as described above. Adrenaline or bronchodilators were added if needed. Epinephrine is recommended if wheezing is present that is not responsive to bronchodilators. Subjects should not receive any further doses of etoposide or carboplatin. This event was reported as an adverse event.

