Patients with first line ES-SCLC: Trilaciclib 240 mg/m² administered intravenously once daily prior to chemotherapy on Days 1 to 3 of each 21-day cycle; carboplatin dose will be calculated according to Calvert formula as target AUC = 5 (maximum 750 mg) on Day 1 and 100 mg/m² etoposide administered intravenously daily on Days 1-3. Patients will receive up to 6 cycles or until disease progression, intolerability, withdrawal of consent, or investigator termination of treatment, whichever occurs first.

Patients with 2nd/3rd line ES-SCLC: Trilaciclib 240 mg/m² IV daily on Days 1 to 5 of each 21-day cycle prior to chemotherapy; Topotecan 1.25 mg/m² on Days 1-5 of each cycle. Study drug will be administered until disease progression, intolerability, withdrawal of consent, or investigator termination of treatment, whichever occurs first.

The study process includes screening period, treatment period, safety follow-up and survival follow-up.

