5.2. Study treatment regimen

The treatment regimen for this study is as follows:

Patients with 1st line ES-SCLC were treated with Trilaciclib or placebo in combination with carboplatin and etoposide (EC regimen); patients with 2nd/3rd line ES-SCLC were treated with Trilaciclib or placebo in combination with topotecan as detailed in Table 4 below:

Investigational drug		Usage	Period of administration		
1st line E	S-SCLC				
EC Regimen	Carboplatin	Target AUC = 5 (maximum dose 750 mg), intravenous drip over 30 min on Day 1 of each 21-day cycle;	Up to 6 cycles *		
Kegimen	Etoposide	100 mg/m ² , 21 days per cycle, intravenous drip over 60 min on days 1-3;	Up to 6 cycles *		
Trilaciclib/Placebo		240 mg/m ² , 21 days per cycle, 30 min intravenous drip before chemotherapy on Days 1-3 (try to complete the drip within 30 + 5 min due to PK study);	Up to 6 cycles *		
* OR Prog	gressive diseas	e, intolerable, withdrawal of consent, or investig	ator discontinuation prior to reaching		
6 cycles, v	whichever cam	e first			
2nd/3rd li	ine ES-SCLC	patients			
Topotecan		1.25 mg/m ² , 21 days per cycle, intravenous drip over 30 min on Days 1-5;	Until disease progression, intolerable, withdrawal of consent, or investigator termination of treatment, whichever came first		
Trilaciclib/Placebo		240 mg/m ² , 21 days per cycle, administered prechemotherapy over 30 min on Days 1-5 (infusion should be completed within $30 + 5$ min if possible due to PK studies).	Until disease progression, intolerable, withdrawal of consent, or investigator termination of treatment, whichever came first		

Table 4	Study	Treatment	Regimen

Date of medication visit is based on the first dose of investigational drug (Trilaciclib/Placebo) in each cycle (D1).

Notes:

Trilaciclib should be administered no more than 28 hours apart between infusions for 3 or 5 consecutive days, and no more than 4 hours between infusions of Trilaciclib and its subsequent injected chemotherapeutic agents (carboplatin or etoposide, or topotecan).

Trilaciclib should be used in combination with chemotherapy, that is, if EC regimen or topotecan is suspended or terminated, then trilaciclib should also be suspended or terminated. Similarly, subsequent chemotherapy should not be administered if the planned administration of Trilaciclib, i.e. Trilaciclib or placebo, has not been completed in any cycle.

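### The 20 mg/h restart rate after a moderate hypersensitivity reaction names no drug, and for topotecan it is about four to six times the full infusion rate

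*Protocol*

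**What the plan says.** Protocol section 5.4.2.2.3 grades hypersensitivity reactions as mild, moderate or life-threatening. For a moderate reaction the infusion is stopped and two drugs are given: "Diphenhydramine 25 mg and dexamethasone 10 mg were administered intravenously". Then: "The infusion was resumed at a low rate (20 mg/h) after recovery of symptoms". The next step is "If no further symptoms appear after 15 min, the rate may be increased to full rate until the infusion is complete". There is also a stop rule: "If symptoms recur, the infusion must be stopped".

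The restart sentence does not say which drug it applies to. The section sits under 5.4.2, which deals with dose modification of the chemotherapy agents and opens "Carboplatin, etoposide, and topotecan should meet neutrophil", so all three drugs are in scope. The only drugs named within 5.4.2.2.3 are in the life-threatening bullet: "Subjects should not receive any further doses of etoposide or carboplatin". Topotecan is neither named nor excluded.

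The topotecan regimen is given in section 3.1 as "Topotecan 1.25 mg/m² on Days 1-5 of each cycle" and in Table 4 of section 5.2 as "21 days per cycle, intravenous drip over 30 min on Days 1-5".

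**The concern.** A single absolute rate in mg/h cannot be low for drugs whose doses differ by a factor of 80 or more: etoposide is given at 100 mg/m² and topotecan at 1.25 mg/m². The purpose of the rule is to re-expose the patient slowly, watch for 15 minutes, and only then speed up. If 20 mg/h is faster than the rate at which the patient reacted, the rule does the opposite of what it intends.

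The patients at stake are those on topotecan who have a moderate reaction and are restarted at a site that sets the pump to the printed number. Topotecan is given on five days of every cycle with no cap on the number of cycles, so the occasion to use the rule recurs. The gap in the life-threatening bullet is a second, related problem: the bar on further dosing omits one of the three drugs. Neither affects the trial's efficacy inference. The total milligrams given do not change, only the speed.

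**Working it through.** The plan gives no full rate in mg/h and no ratio, so there is no figure of its own to reproduce. The check is direct arithmetic.

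**Inputs**
- Restart rate 20 mg/h and step-up check at 15 min: section 5.4.2.2.3.
- Topotecan 1.25 mg/m² over 30 min (0.5 h): sections 3.1 and 5.2. Reduced doses 1 and 0.8 mg/m²: Table 5, section 5.4.2. I assume the 30-minute infusion also applies at the reduced doses.
- Etoposide 100 mg/m² over 60 min; carboplatin AUC 5, capped at 750 mg, over 30 min: section 5.2.
- Assumed, not in the documents: body surface area (BSA) 1.4 to 2.0 m²; GFR 60 to 125 mL/min for carboplatin.

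**Topotecan.** Full rate = dose per m² × BSA / 0.5 h. Ratio = 20 / full rate.

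| Dose (mg/m²) | Full rate, BSA 1.4 | Full rate, BSA 2.0 | 20 mg/h as a multiple of full rate |
|---|---|---|---|
| 1.25 | 3.5 mg/h | 5.0 mg/h | 5.7 to 4.0 |
| 1.0 | 2.8 mg/h | 4.0 mg/h | 7.1 to 5.0 |
| 0.8 | 2.24 mg/h | 3.2 mg/h | 8.9 to 6.3 |

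**Dependence on the BSA assumption.** At 1.25 mg/m² the full rate is 2.5 mg/m²/h, so 20 mg/h equals full rate only at 20 / 2.5 = 8 m². In 15 minutes 20 mg/h delivers 20 × 0.25 = 5 mg, so a whole 1.25 mg/m² dose lasts to the 15-minute check only at 5 / 1.25 = 4 m² or more. The direction of the result holds at any realistic BSA.

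**Time to finish at 20 mg/h, 1.25 mg/m².**
- Whole dose, 1.75 to 2.5 mg: 1.75 / 20 × 60 = 5.3 min to 2.5 / 20 × 60 = 7.5 min.
- Reaction at 5 min: remainder = dose × 25/30 = 1.46 to 2.08 mg, run in 4.4 to 6.3 min instead of 25.
- Reaction at 25 min: remainder = dose × 5/30 = 0.29 to 0.42 mg, run in 0.9 to 1.3 min instead of 5.

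In every case the infusion is over before the 15-minute point.

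**Comparison drugs.**
- Etoposide: full rate 140 to 200 mg/h, so 20 mg/h is 14% to 10% of it.
- Carboplatin, Calvert formula: 5 × (60 + 25) = 425 mg to 5 × (125 + 25) = 750 mg, over 0.5 h = 850 to 1,500 mg/h, so 20 mg/h is 2.4% to 1.3% of it.

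The number is sensible for these two drugs and wrong for topotecan.

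**How many patients.** The documents give no topotecan hypersensitivity rate. The nearest figure is infusion-related reaction in section 1.3.1: 8.2% with trilaciclib and 1.7% with placebo, each with chemotherapy, pooled over regimens and grades. No split between regimens is fixed; assuming 20 to 60 of the 80 Part II patients receive topotecan, 1.7% gives 0.3 to 1.0 patients with any such reaction. Averaging the two arms, (1.7% + 8.2%) / 2 = 4.95%, gives 1.0 to 3.0. That is a loose upper figure, because the trilaciclib excess may be due to trilaciclib itself. Moderate, topotecan-attributed, restarted cases would be fewer.

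**The case against.** The strongest reply is that the sentence was never meant for topotecan. Elsewhere under 5.4.2 the drafters name topotecan when they mean it, whereas 5.4.2.2.3 names only etoposide and carboplatin. Section 5.6 shows the same carboplatin-etoposide drafting in its cautions. The sentence also calls 20 mg/h low and allows it to rise to full rate, which makes no sense for a bag holding about 2 mg, so staff should notice. This is probably the drafting history. But no text limits the rule to that regimen, and a site looking for guidance on a topotecan reaction would find this paragraph.

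Nor would the narrower reading solve the problem. Topotecan reactions would then fall to the general rules in 5.4.2.3: hold until recovery, then resume at the same dose for a first Grade 2 event or at a reduced dose for an unlisted Grade 3 or 4 event. Those rules give no infusion rate. They could also be read as pointing to rechallenge after a severe topotecan reaction, when the same reaction to etoposide or carboplatin bars further doses. The investigator can still stop treatment under 5.5.1, so nobody is obliged to rechallenge.

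Other safeguards are real. Patients with known topotecan hypersensitivity are excluded. Restart follows recovery and premedication. Recurrence stops the infusion and bars further chemotherapy in that cycle. Section 5.4.2.3 calls the scheme recommended and allows the package insert to be used with reasons recorded. Section 11.1.3 has qualified staff working from drug instructions and a manual, which I have not seen. Reactions to trilaciclib itself are sent to the Investigator's Brochure by 5.5.1.1. These lower the risk, but they rely on someone departing from the printed number. The recurrence stop also protects less when the remainder may be in within about 1 to 6 minutes.

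**Conclusion.** The concern holds. As written, the restart rule gives one absolute rate for a section that covers three drugs, and for topotecan that rate is 4.0 to 5.7 times full rate at the starting dose and up to 8.9 times at the lowest dose (BSA 1.4 to 2.0 m², 30-minute infusion). The exact multiple rests on the BSA assumption; the conclusion that 20 mg/h is above full rate does not. Whether a site would apply it to topotecan depends on how it reads an unstated scope, but the alternative reading leaves topotecan with no restart rate. In both readings topotecan is missing from the bar on further doses after a life-threatening reaction. This is a patient-safety point of low expected frequency, with no bearing on the primary endpoint, power or type I error. It should be corrected because the instruction is numerically wrong for one of the two regimens.

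**What to change.** - State that the 20 mg/h restart applies to etoposide and carboplatin only.
- For topotecan, either set the restart rate as a fraction of its own full rate (2.5 mg/m²/h at the starting dose, 2.0 and 1.6 mg/m²/h at dose levels -1 and -2) or refer to its package insert. As an illustration only, one tenth of full rate at the starting dose is 0.25 mg/m²/h, that is 0.35 to 0.5 mg/h. Over 15 minutes this delivers 0.0875 to 0.125 mg, or 5% of a 1.75 to 2.5 mg dose. The sponsor's clinical team should choose the rate.
- Add topotecan to the drugs that may not be given again after a life-threatening reaction.

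The cost is one paragraph in a protocol amendment or a letter to sites, with no extra data, visits or patients.
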